**Description:**

- The purpose of this RAP is to describe the planned analyses and output to be included in the Clinical Study Report for Protocol 207660.
- This RAP is intended to describe the efficacy and safety analyses required for the study.
- This RAP will be provided to the study team members to convey the content of the interim and final Statistical Analysis Complete (SAC) deliverable.

## CONFIDENTIAL

207660

## 1. INTRODUCTION

### 1.1. Summary of Key Protocol Information

#### 1.1.1. Changes to the Protocol Defined Statistical Analysis Plan

There were no changes or deviations to the originally planned statistical analysis specified in the protocol amendment 02 [(Dated: 06OCT2017)].

#### 1.1.2. Study Objective(s) and Endpoint(s)

Objectives	Endpoints
Primary Objectives	Primary Endpoints

 
To evaluate the efficacy of the injections of 400 units of the product at Week 6 (finger/ wrist flexors: 240 units, elbow flexors: 160 units), comparing to that of 240 units (finger/ wrist flexors: 240 units, elbow flexors: placebo).
 
	
 
The responder rate: The rate of the participants that Modified Ashworth Scale (MAS) score was reduced at least 1 from baseline in the elbow flexors.
 

Secondary Objectives	Secondary Endpoints

 
To evaluate the efficacy of 400 units of the product, comparing to 240 units of the product
 
	
 
The responder rate of MAS score from baseline in the finger, thumb and wrist flexors
 
Changes in MAS score from baseline in the finger, thumb, wrist and elbow flexors
 
Changes in Disability Assessment Scale (DAS) from baseline
 

 
To evaluate the safety and tolerability of the product of 400 units, comparing to 240 units of the product/ To evaluate the safety and tolerability of 400 units of the product
 
	
 
Adverse events
 
Physical examinations
 
Clinical laboratory tests (haematology, blood biochemistry, urinalysis)
 
Vital signs (heart rate, blood pressure, body temperature)
 

Exploratory Objectives	Exploratory Endpoints

 
To evaluate the efficacy of 400 units of the product
 
	
 
Changes in MAS score from baseline in finger, thumb, wrist, elbow, pronation of the forearm and shoulder flexors
 


 
To evaluate the other efficacy of the product of 400 units, comparing to 240 units of the product/ To evaluate the other efficacy of 400 units of the product
 
	
 
Changes in Numeric Rating Scale (NRS) for pain from baseline
 
Changes in other items of DAS from baseline
 
Clinical Global Impression of Change (CGI) of functional disability by an investigator
 
CGI of functional disability by a patient
 
Time to patient-reported onset of spasticity symptom relief
 
Patient-reported benefit of injection
 
Time to qualification for retreatment
 

Objectives	Endpoints

 
To evaluate neutralizing antibody production
 
	
 
Testing for neutralizing antibody
 

**1.1.3. Study Design**

Overview of Study Design and Key Features	
Design Features	
This study includes a Screening Phase, Blind Phase, and Open-label Phase. The study design of each treatment phase is shown below.
 
 
Blind Phase: Multicenter, randomized, double-blind, placebo-controlled, parallel-group comparison design
 
Open-Label Phase: Multicenter, uncontrolled, open-label design
 

Dosing	
 
In the Blind Phase, participants will be randomly assigned 1:1 to either the 400 or the 240-unit group.                             
 
In the 400-unit group, 240 units of the product will be injected into the muscles that act on the finger (including thumb flexors) and wrist flexors, and 160 units into the muscles that act on the elbow flexors. A total of 400 units of the product will be injected.
 
In the 240-unit group, 240 units of the product will be injected into the muscles that act on the finger (including thumb flexors) and wrist flexors. Placebo will be injected into the muscles that act on the elbow flexors. A total of 240 units of the product will be injected.
 
 
 
In the Open-label phase, a total of 400 units will be injected in both groups.                             
 
The product can be injected up to 3 times after completion of Part 1 in the blind phase. Participants whom the investigator considers as eligible for the injections will be treated. The next injections cannot be performed until the eligibility of the participant has been confirmed by the investigator.
 
The muscle to be injected and the dose will be decided by the investigator based on the patient's symptoms, and a total dose of 400 units of the product will be injected in a divided dose. For the muscles that the investigator considers as unnecessary to be treated, an injection may be skipped. The involving muscle and the dose do not have to be same each time always.
 
 
 

CONFIDENTIAL

207660

Overview of Study Design and Key Features	
Treatment Assignment	
 
• Number of participants (randomized participants): 120 (60 per group)
 
• GSK RandAll NG will be used to generate the randomization schedule.
 
• The randomization will be stratified by the MAS score (3 or 4) in the elbow flexors at Day1
 

Interim Analysis	
 
• Interim analysis is planned in this study as described in 3.1.
 

#### **1.1.4. Statistical Hypotheses / Statistical Analyses**

No formal hypothesis will not be tested.

## **2. PLANNED ANALYSES**

### **2.1. Interim Analyses**

The interim planned primary analyses will be performed after the completion of the following sequential steps:

1. All participants (except for early termination) complete the visit at Week 24 of the initial dose as defined in the protocol. The participants who complete that visit are defined as below.

The participant is re-treated at Week 12 visit in Blind Phase and completes the Week 12 visit in Open-label Phase.

The participant is re-treated at Week 16 visit in Blind Phase and completes the Week 12 visit in Open-label Phase.

The participant is re-treated at Week 20 visit in Blind Phase and completes the Week 4 visit in Open-label Phase.

The participant completes the Week 24 visit in Blind Phase.

2. All required database cleaning activities have been completed and interim database release and database freeze has been declared by Data Management.
3. All criteria for unblinding the randomization codes have been met.
4. Randomization codes have been distributed according to RandAll NG procedures.
5. Interim analyses will be performed.

The interim analyses will be performed for regulatory submission. However subject level data will not be disclosed to people who work at the sites including investigators.

All planned interim analyses (i.e. Study population, Efficacy and Safety analyses) will be performed using data up to Week 24 visit for all participants.

For Adverse Events, Cardiovascular Events, Liver Events and Medication, the data up to Week 24 visit is defined by using the start date. If the start date of these data is earlier

## CONFIDENTIAL

207660

than or same as the date of Week 24 visit defined above, these data will be included in the data up to Week 24 visit. Otherwise the data will not.

## 2.2. Final Analyses

The final planned primary analyses will be performed after the completion of the following sequential steps:

1. All participants have completed the study as defined in the protocol.
2. All required database cleaning activities have been completed and final database release and database freeze has been declared by Data Management.
3. Final analyses will be performed.

## 3. ANALYSIS POPULATIONS

Population	Definition / Criteria	Analyses Evaluated
Screened	
 
• Comprise of all screened participants
 
	
 
• Study Population
 

Enrolled	
 
• Comprise of all participants who meet the eligibility criteria at a screening and Day 1 visit.
 
	
 
• Study Population
 

Intent-To-Treat 1 (ITT1)	
 
• This population consists of all participants who are randomized in the study and who have at least 1 post-baseline efficacy assessment:
 
• ITT is the primary efficacy analysis population, and the participants will be analyzed in line with the randomized treatment group
 
• Any participant who receives a study treatment randomization number will be considered to have been randomized.
 
	
 
• Study Population
 
• Efficacy
 

ITT2	
 
• This population consists of all participants in ITT1 population, who have at least 2 study treatments and who have at least 1 efficacy assessment after the 2nd treatment.
 
	
 
• Study Population
 
• Efficacy
 

ITT3	
 
• This population consists of all participants in ITT2 population, who have at least 3 study treatments and who have at least 1 efficacy assessment after the 3rd treatment.
 
	
 
• Study Population
 
• Efficacy
 

ITT4	
 
• This population consists of all participants in ITT3 population, who have 4 study treatments and who have at least 1 efficacy assessment after the 4th treatment.
 
	
 
• Study Population
 
• Efficacy
 

CONFIDENTIAL

207660

Population	Definition / Criteria	Analyses Evaluated
Safety1	
 
This population consists of all participants who are randomized in the study and who receive study treatment at least once
 
The participants will be analyzed based on the treatment actually given.
 
	
 
Safety
 

Safety2	
 
This population consists of all participants in Safety1 population, who receive study treatment at least twice.
 
The participants will be analyzed based on the treatment actually given.
 
	
 
Safety
 

Safety3	
 
This population consists of all participants who are randomized in the study and who receive study treatment at least three times
 
The participants will be analyzed based on the treatment actually given.
 
	
 
Safety
 

Safety4	
 
This population consists of all participants in Safety1 population, who receive study treatment four times.
 
The participants will be analyzed based on the treatment actually given.
 
	
 
Safety
 

**NOTES :**

- Please refer to [Appendix 12: List of Data Displays](#) which details the population to be used for each displays being generated.

**3.1. Protocol Deviations**

Important protocol deviations (including deviations related to study inclusion/exclusion criteria, conduct of the trial, patient management or patient assessment) will be summarised and listed.

Protocol deviations will be tracked by the study team throughout the conduct of the study in accordance with the Protocol Deviation Management Plan.

- Data will be reviewed prior to unblinding and freezing the database to ensure all important deviations are captured and categorised on the protocol deviations dataset.
- This dataset will be the basis for the summaries and listings of protocol deviations.

A separate listing of all inclusion/exclusion criteria deviations will also be provided. This listing will be based on data as recorded on the inclusion/exclusion page of the eCRF.

## CONFIDENTIAL

207660

## 4. CONSIDERATIONS FOR DATA ANALYSES AND DATA HANDLING CONVENTIONS

### 4.1. Study Treatment & Sub-group Display Descriptors

Treatment Group Descriptions			
RandAll NG		Data Displays for Reporting	
Code	Description	Description	Order in TLF
A	GSK1358820 240U	GSK1358820 240U	1
B	GSK1358820 400U	GSK1358820 400U	2

Treatment comparisons will be displayed as follows using the descriptors as specified:

1. GSK1358820 400U vs GSK1358820 240U

### 4.2. Baseline Definitions

For all endpoints (except as noted in baseline definitions) the baseline value will be the latest pre-dose assessment with a non-missing value, including those from unscheduled visits. If time is not collected, Day 1 assessments are assumed to be taken prior to first dose and used as baseline. These baseline values will be used for all analyses in both Blind Phase and Open Label Phase.

Unless otherwise stated, if baseline data is missing no derivation will be performed and baseline will be set to missing.

### 4.3. Multicentre Studies

No data will be analysed by center.

### 4.4. Examination of Covariates, Other Strata and Subgroups

#### 4.4.1. Covariates and Other Strata

The list of covariates and other strata may be used in descriptive summaries and statistical analyses, some of which may also be used for subgroup analyses. Additional covariates and other strata of clinical interest may also be considered.

Category	Details
Strata and Covariates	Baseline MAS value (3 or 4)

#### 4.4.2. Examination of Subgroups

The list of subgroups may be used in descriptive summaries and statistical analyses. Additional subgroups of clinical interest may also be considered.

## CONFIDENTIAL

207660

- If the percentage of participants is small within a particular subgroup, then the subgroup categories may be refined prior to unblinding the trial.
- If the category cannot be refined further, then descriptive rather than statistical comparisons may be performed for the particular subgroup.

Subgroup	Categories
Baseline MAS value	3 or 4
Baseline Rehabilitation	
Task-specific practice	Yes, or No The subgroup analyses will be conducted by each rehabilitation use.
Muscle strengthening exercise	
Stretching/Range of motion exercise	
Splinting/Orthoses	
Taping	
Positioning aids	

#### 4.5. Multiple Comparisons and Multiplicity

No multiplicity adjustment is considered in this study because no statistical hypothesis will be tested.

#### 4.6. Other Considerations for Data Analyses and Data Handling Conventions

Other considerations for data analyses and data handling conventions are outlined in the appendices:

Section	Component
Section 9.3	Appendix 3: Assessment Windows
Section 9.4	Appendix 4: Study Phases and Treatment Emergent Adverse Events
Section 9.5	Appendix 5: Data Display Standards & Handling Conventions
Section 9.6	Appendix 6: Derived and Transformed Data
Section 9.7	Appendix 7: Reporting Standards for Missing Data
Section 9.8	Appendix 8: Values of Potential Clinical Importance

## **5. STUDY POPULATION ANALYSES**

### **5.1. Overview of Planned Study Population Analyses**

The study population analyses will be based on the Screened, Enrolled and ITT populations, unless otherwise specified.

Study population analyses including analyses of participant's disposition, protocol deviations, demographic and baseline characteristics, prior and concomitant medications, and rehabilitations will be based on GSK Core Data Standards. Details of the planned displays are presented in [Appendix 12: List of Data Displays](#).

### **5.2. Participant Disposition and Population**

The number and percentage of those participants below will be presented by treatment group and total.

- Participants who completed the Week 24 and who withdrew early from study by Week 24 (including the reasons for early withdrawal)
- Participants who completed the study and who withdrew early from study (including the reasons for early withdrawal)
- Participants who passed screening and who failed screening (including the reasons for screen failure)
- Participants at each centre
- Participants included in each population defined in the Section 3.

These items below will be listed.

- The reasons for early withdrawal and screen failure.
- Participants who were rescreened.
- Participants for whom the treatment blind was broken.
- Planned and actual treatments
- Participants excluded from any population defined in the Section 3.

### **5.3. Protocol Deviation**

The number and percentage of participants with important protocol deviation will be presented by treatment group. This summary will not include subcategories

Important protocol deviations and participants with inclusion/exclusion criteria deviation will be listed.

### **5.4. Demographic and Baseline Characteristics**

These parameters as below will be summarized by treatment group and total.

- Demographic data (age, sex, ethnicity, weight, height, body mass index(BMI), race and racial combinations)

**CONFIDENTIAL**

207660

- Baseline Efficacy Parameter
  - Modified Ashworth Scales in finger, thumb, wrist, elbow, pronation of forearm and shoulder flexors.
  - Numeric Rating Scale for pain
  - Disability Assessment Scale (Main Assessment Parameter)
  - Disability Assessment Scale (Hygiene, Pain, Dressing and Limb posture)
  - The selected item as a Main Assessment Parameter of DAS out of the 4 items
    - Hygiene
    - Pain
    - Dressing
    - Limb posture

**5.5. Prior and Concomitant Medications**

All medication used in this study will be coded according to drug name as defined in the GSK Drug Dictionary. The relationship between the ATC level 1 and ingredient will be summarized for the all prior and concomitant medications, respectively.

**5.6. Rehabilitation**

- Screening

The number and percentage of Rehabilitations will be presented.

- Treatment phase

The category and frequency of Rehabilitations will be collected on eCRF. The number and percentage of each Rehabilitation will be presented in Blind Phase. The category and frequency of Rehabilitations in all treatment phase will be listed.

- Category and Frequency

The categories of Rehabilitation are as below:

- Task-specific practice
- Muscle strengthening exercise
- Stretching/Range of motion exercise
- Splinting/Orthoses
- Taping
- Positioning aids

CONFIDENTIAL

207660

- Other

The category of frequency which will be collected on CRF is defined as below:

- No practice
- > 8 days per month
- > 8 and  $\leq$  16 days per month
- > 16 and  $\leq$  24 days per month
- > 24 days per month

## **6. EFFICACY ANALYSES**

### **6.1. Primary Efficacy Analyses**

#### **6.1.1. Endpoint / Variables**

The primary endpoint is the responder rate of MAS score.

#### **6.1.2. Summary Measure**

The summary measure is the difference in the responder rate of MAS score.

#### **6.1.3. Population of Interest**

The primary efficacy analyses will be based on the Intent-To-Treat 1 population, unless otherwise specified.

#### **6.1.4. Strategy for Intercurrent (Post-Randomization) Events**

Intercurrent event: early withdrawal from study

Strategy : if MAS score is missing because of an early withdrawal from the study, the participant will be regarded as a non-responder.

#### **6.1.5. Statistical Analyses / Methods**

Details of the planned displays are provided in [Appendix 12: List of Data Displays](#) and will be based on GSK data standards and statistical principles.

Unless otherwise specified, endpoints / variables defined in Section [6.1.1](#) will be summarised using descriptive statistics and listed.

## CONFIDENTIAL

207660

**6.1.5.1. Statistical Methodology Specification**

Endpoint / Variables

 
• Responder Rate of MAS in the elbow flexors at Week 6 of the initial dose
 

Model Specification

 
• To summarize the primary endpoint without statistical model 
 
○ The primary endpoint will be calculated as the proportion of participants whose MAS score decreased by at least 1 level from the baseline in the ITT1 population.
 
○ The intergroup difference in the responder rate and its 95% confidence interval (Wald-type) will be computed.
 
 
 

Data Convention

 
• The MAS scores, 0, 1, 1+, 2, 3 and 4 will be encoded to 0, 1, 2, 3, 4 and 5, respectively, for the analyses.
 

Definition of Responder and Responder rate

“Responder” is defined as a participant whose MAS score decrease by at least 1 level from the baseline.
 
Responder Rate will be calculated as below.
 $\text{Responder Rate (\%)} = (\text{Number of Respondersparticipant}) / (\text{Number of participants in ITT1 population}) \times 100$ 
 
• If MAS score of a given participant is missing at Week 6, then this participants will be regarded as a non-responder.
 

Model Results Presentation

 
• The difference in the responder rate (400 units – 200 units) and its associated 95% CI will be presented.
 

Subgroup Analyses (Rehabilitation)

 
• Subgroup analyses will be performed by baseline rehabilitation in the Section 4.4.
 
• The difference (400 units – 200 units) and its 95% CI will be presented.
 

Subgroup Analyses (baseline MAS score)

 
• Subgroup analyses will be performed by baseline MAS score (3 or 4).
 
• The difference (400 units – 200 units) and its 95% CI will be presented.
 

Supportive Analyses

 
• The difference in the responder rate will be estimated using Mantel-Haenszel method to consider a stratification factor, that is baseline MAS score (3 or 4).
 
• Mantel-Haenszel rate difference (400 units – 200 units) and its 95% CI will be calculated.
 

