### 2.3. Study Design

Overview of Study Design and Key Features	

The diagram illustrates the study design timeline. It begins with a 'Screening' phase. This is followed by a 'Double-blind treatment' phase lasting 12 weeks, labeled as 'Part 1'. In this phase, participants are randomized to receive either 'BOTOX 400 U' or 'BOTOX 240 U + Placebo'. After the double-blind phase, the study enters an 'Open-label treatment' phase lasting 36 weeks, which is divided into three parts: 'Part 2', 'Part 3', and 'Part 4'. All participants in the open-label phase receive 'BOTOX 400 U'. Arrows labeled 'dose' indicate the timing of each injection.
	
Design Features	
This study includes a Screening Phase, Blind Phase, and Open-label Phase. The study design of each treatment phase is shown below.
 
 
Blind Phase: Multicenter, randomized, double-blind, placebo-controlled, parallel-group comparison design
 
Open-Label Phase: Multicenter, uncontrolled, open-label design
 

Dosing	
 
In the Blind Phase, participants will be randomly assigned 1:1 to either the 400 or the 240-unit group.
 
In the 400-unit group, 240 units of the product will be injected into the
 

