## CONFIDENTIAL

207660

Overview of Study Design and Key Features	
	
muscles that act on the finger (including thumb flexors) and wrist flexors, and 160 units into the muscles that act on the elbow flexors. A total of 400 units of the product will be injected.
 
 
• In the 240-unit group, 240 units of the product will be injected into the muscles that act on the finger (including thumb flexors) and wrist flexors. Placebo will be injected into the muscles that act on the elbow flexors. A total of 240 units of the product will be injected.
 
• In the Open-label phase, a total of 400 units will be injected in both groups. 
 
• The product can be injected up to 3 times after completion of Part 1 in the blind phase. Participants whom the investigator considers as eligible for the injections will be treated. The next injections cannot be performed until the eligibility of the participant has been confirmed by the investigator.
 
• The muscle to be injected and the dose will be decided by the investigator based on the patient's symptoms, and a total dose of 400 units of the product will be injected in a divided dose. For the muscles that the investigator considers as unnecessary to be treated, an injection may be skipped. The involving muscle and the dose do not have to be same each time always.
 
 
 

Treatment Assignment	
 
• Number of participants (randomized participants): 120 (60 per group)
 
• GSK RandAll NG will be used to generate the randomization schedule.
 
• The randomization will be stratified by the MAS score (3 or 4) in the elbow flexors at Day1
 

Interim Analysis	
 
• Interim analysis is planned in this study as described in 3.1.
 

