**7.1.5.1. Statistical Methodology Specification**

Endpoint / Variables

 
• Responder Rate of MAS in the elbow flexors at Week 6 of the initial dose
 

Model Specification

 
• To summarize the primary endpoint without statistical model 
 
○ The primary endpoint will be calculated as the proportion of participants whose MAS score decreased by at least 1 level from the baseline in the ITT1 population.
 
○ The intergroup difference in the responder rate and its 95% confidence interval (Wald-type) will be computed.
 
 
 

Data Convention

 
• The MAS scores, 0, 1, 1+, 2, 3 and 4 will be encoded to 0, 1, 2, 3, 4 and 5, respectively, for the analyses.
 

Definition of Responder and Responder rate

“Responder” is defined as a participant whose MAS score decrease by at least 1 level from the baseline.
 
Responder Rate will be calculated as below.
 
Responder Rate (%) = (Number of Responders) / (Number of participants in ITT1 population) x 100
 
 
• If MAS score of a given participant is missing at Week 6, then this participant will be regarded as a non-responder.
 

Model Results Presentation

 
• The difference in the responder rate (400 units – 240 units) and its associated 95% CI will be presented.
 

Subgroup Analyses (Rehabilitation)

 
Subgroup analyses will be performed by baseline rehabilitation in the Section 5.4.
 
The difference (400 units – 240 units) and its 95% CI will be presented.
 

Subgroup Analyses (baseline MAS score)

 
Subgroup analyses will be performed by baseline MAS score of the elbow (3 or 4) used as randomization strata.
 
The difference (400 units – 240 units) and its 95% CI will be presented.
 

Supportive Analyses

 
The difference in the responder rate will be estimated using Mantel-Haenszel method to consider a stratification factor, that is baseline MAS score of the elbow (3 or 4).
 
Mantel-Haenszel rate difference (400 units – 240 units) and its 95% CI will be calculated.
 

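### The amended RAP gives a separate 400−240 difference for each rehabilitation and elbow-MAS level but no contrast between levels, so a constant effect of about 20–30 points could readily look rehabilitation-dependent

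*SAP*

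**What the plan says.** The current text is the amended RAP of 20 August 2018. Section 7.1.5.1 states "Subgroup analyses will be performed by baseline rehabilitation in the Section 5.4" and, for the stratification factor, "Subgroup analyses will be performed by baseline MAS score of the elbow (3 or 4) used as randomization strata". For each it specifies one output: "The difference (400 units – 240 units) and its 95% CI will be presented". The interval method for the primary endpoint is given in the same section: "The intergroup difference in the responder rate and its 95% confidence interval (Wald-type) will be computed".

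Section 5.4.2 lists six rehabilitation types (task-specific practice, muscle strengthening, stretching/range of motion, splinting/orthoses, taping, positioning aids), each Yes or No, and says "The subgroup analyses will be conducted by each rehabilitation use". It adds that categories of small subgroups may be refined before unblinding. If that is not possible, a descriptive rather than a statistical comparison may be used. No size threshold is given.

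The original RAP of 2 April 2018 has the same structure in 6.1.5.1: "Subgroup analyses will be performed by baseline rehabilitation in the Section 4.4". The amendment changed the cross-reference, the 200/240-unit label and the words identifying the elbow. It added no contrast.

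The results go into Table 2.03, part of the interim package that Section 3.1 says is for regulatory submission. Sections 2.4 and 5.5 say that no hypothesis is tested and that no multiplicity adjustment is made.

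**The concern.** A subgroup analysis asks whether the treatment effect differs between levels. Two separate intervals do not answer that. One can exclude 0 and the other include it merely because one level is smaller, or because each level has about half the sample and limited precision.

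With 14 intervals from 120 participants, a reader of Table 2.03 could see an interval above 0 for, say, stretching Yes and one crossing 0 for stretching No. That reader could infer that the elbow injection works only alongside that therapy, when the data show no such difference. The quantity that would correct this reading, the difference between the two differences, is not among the planned outputs.

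**Working it through.** **Inputs from the RAP.** 120 randomized, 60 per group, 1:1 (Section 2.3). Wald 95% CI (7.1.5.1). Six Yes/No rehabilitation types plus MAS 3 or 4 (5.4.2), so 7 factors × 2 levels = 14 intervals. The RAP attaches no responder rates or power to the 120, so there is no figure of its own to reproduce.

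**Inputs assumed.** Responder rates and rehabilitation uptake are not in the document, so both are varied.

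**Is there a contrast anywhere?** The only interaction terms are treatment-by-visit and baseline-by-visit in the MMRM (7.2.5.1). The Mantel-Haenszel difference in 7.1.5.1 pools over the two MAS strata and does not compare them. No homogeneity or interaction analysis is listed.

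**One pair by hand, constant rates 40% vs 70%.** Within a level with n per arm, SE = √[(0.40×0.60 + 0.70×0.30)/n] = √(0.45/n). The chance that its interval lies above 0 is about Φ(0.30/SE − 1.96).

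- Even split, n = 30 in each level: SE = 0.1225, so 0.30/SE = 2.45 and Φ(0.49) = 0.69. Discordant intervals: 2 × 0.69 × 0.31 = 0.43. Simulation gave 0.44.
- 20/80 split, n = 12 and 48: SE = 0.194 and 0.097, giving Φ(−0.41) = 0.34 and Φ(1.14) = 0.87. Discordant: 0.34 × 0.13 + 0.66 × 0.87 = 0.62.

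**Six rehabilitation types together.** Simulation with 3,000 trials per scenario, 60 per arm and the same risk difference in everyone. Uptake was 50% in each type, 30% in each type, mixed (10–80%) or skewed (5–90%), with latent correlation between types of 0 or 0.5. The last column is the chance that at least one type has one interval excluding 0 and the other including it.

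| Constant effect (points) | At least one discordant type |
|---|---|
| 10 | 50–71% |
| 20 | 79–90% |
| 25 | 84–96% |
| 30 | 74–98% |
| 40 | 39–95% |
| 50 | 10–88% |
| 60 | 1–73% |

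The low ends at 40 points or more come from 50% uptake in every type: 39–42% at 40 points, 10–11% at 50 and 1% at 60. For scale, 60 per arm has 61% power for 50% vs 70% and 94% for 50% vs 80%. The MAS pair alone is discordant in 44–63% of trials at 20–30 points, and in 15–49% at 40% vs 80%.

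**What a direct contrast does.** Its variance is the sum of the two subgroup variances. Half-widths at 40/70:

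- Even split: 1.96 × √(0.45/30 + 0.45/30) = 0.34.
- 20/80 split: 1.96 × √(0.45/12 + 0.45/48) = 0.42.

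At 20–30 points and 50% uptake, the false signal for one pair falls from about 39–51% (discordant intervals) to about 5–6% (contrast excludes 0). It is about 9–10% when the smaller level holds 15% of participants. For six independent contrasts the nominal chance of at least one false signal is 1 − 0.95⁶ = 26.5%. Simulation gave 25–34% at 50% or 30% uptake, and up to about 65% with sparse levels kept. For all seven factors, with assumed shares of 50, 30, 30, 70, 30, 20 and 20% and cells below 5 per arm dropped, it was 35–39%.

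**The case against.** The strongest reply is that the RAP tests nothing and nowhere says that a subgroup effect is judged by whether an interval covers 0. Counting discordant intervals imposes a significance reading that the plan does not adopt. Point estimates and interval widths are all shown, and anyone can compute the contrast from them, so no information is lost. Small levels may be handled descriptively under 5.4.2. The contrasts are so imprecise that they will settle little.

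Much of this stands. It is why the point concerns presentation and is not an error in the primary analysis. It does not remove the gap. Section 5.4.2 makes a descriptive comparison the fallback for small subgroups, so statistical comparison is the default. The fallback is optional, has no threshold and supplies no contrast. An added estimate with its interval fits an estimation-only plan. Wide contrast intervals are themselves informative, because they show how little 120 participants can say about effect modification.

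A reader might go further and infer that a constant effect will very likely look rehabilitation-dependent whatever its size. The document does not support that. It gives neither responder rates nor uptake, and the probability ranges from 1% to 98% over plausible values.

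**Conclusion.** The structural point holds in full on the amended text: separate within-level intervals only, and no contrast between levels for any of the seven factors.

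Its size is conditional. For a constant effect of about 20–30 points, roughly 75–98% of trials would show at least one rehabilitation type with discordant intervals. That range rests on the assumed rates and uptake patterns and refers to the six types jointly. It should not be read as the chance for any one named type, nor for the MAS factor, where the chance at these effects is nearer a coin toss.

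The primary responder difference, its CI and the Mantel-Haenszel analysis are untouched. This is a cheap improvement to what the subgroup table can support.

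**What to change.** In amended Section 7.1.5.1 and Table 2.03, add for each of the seven factors the difference between the two subgroup differences: 400−240 in Yes minus 400−240 in No, and MAS 4 minus MAS 3. Give its 95% CI, with variance equal to the sum of the two subgroup variances. State that any suggestion of a differing effect is read from these contrasts, taken jointly and as exploratory, and not from whether the separate intervals cover 0.

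The cost is a short addition to the text and one column in the table, with no new data. The downside is the imprecision and chance findings quantified above, which is why no single contrast should serve as a decision rule.
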